### TREATMENT PHASE:

Patients in both groups will receive an interscalene nerve block with 20 mL 0.5% bupivacaine. Subjects in the Pecs II block group will receive 20mL 0.25% bupivacaine; 20ml will be injected between pectoralis minor and serratus anterior muscles. The subpectoral surgical skin infiltration group will receive 15mL bupivacaine 0.25% by the surgeon. These medications will be obtained from the operating room omniceil. Neither the anesthesiologist nor surgeon will be blinded to the patient's group assignment, as they are the ones administering the treatment. All other stakeholders (patient, other caregivers, and research staff collecting the data) will be blinded to the patient's group assignment.

[figure not shown]
### POST-OPERATIVE PHASE:

After initial recruitment, subjects' pain will be assessed via visual analog scale (VAS) by nursing staff during the post-operative period as per standard of care. The VAS pain scores are collected and documented in the patient's electronic medical record. Additionally, a standardized regimen of pain medication will be given to all subjects who are enrolled. The pain medications given to patients are standard of care medications and vary based on pain level. This is determined by the clinical staff caring for each patient. While the patient is in the PACU, an authorized research member will visit the patient and obtain a pain score using the Numeric Rating Scale (NRS) and McGill Pain Scale. Skin testing in the axilla will be done in PACU prior to discharge to evaluate the presence or absence of sensation in that area. Data on PACU opioid use documented in EPIC will be collected. On POD1 and POD 3, a phone call to the patient will be made to collect additional data on oxycodone use at home as well as an NRS score at 24 and 72 hours after surgery.

## 2.2 Schematic of Study Design

CONFIDENTIAL

This material is the property of the NYU School of Medicine and Langone Medical Center. Do not disclose or use except as authorized in writing by the study sponsor

Interventional Template Version: 11 January 2019

### **3 Study Enrollment and Withdrawal**

The researchers will approach patients scheduled for shoulder arthroscopy with open biceps tenodesis who are eligible for participation in the study. Anesthesiology attendings, fellows, residents, and authorized researchers will consent and enroll patients pre-operatively.

#### **3.1 Inclusion Criteria**

1. Patients between 18 and 75 years of age
2. Patients undergoing shoulder arthroscopy with open subpectoral biceps tenodesis

#### **3.2 Exclusion Criteria**

1. Patients younger than 18 and older than 75;
2. Patients with a history of chronic pain that have used opioids for pain management for 3 months or longer;
3. Patients who are allergic to oxycodone;
4. Patients with diagnosed or self-reported cognitive dysfunction;
5. Patients with a history of neurologic disorder that can interfere with pain sensation;
6. Patients with a history of drug or recorded alcohol abuse;
7. Patients who are unable to understand or follow instructions;
8. Patients with severe liver disease, renal insufficiency, congestive heart failure, and/or significant heart disease;
9. Patients with an allergy or contraindication to any of the medications used in the study, or patients with a contraindication to any study procedures;
10. Patients with a BMI over 45;
11. Any patient that the investigators feel cannot comply with all study related procedures;
12. NYU Langone Health students, residents, faculty or staff members.

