### 1.3 Objectives and Purpose

The goal of this study is to compare the postoperative pain control using a Pecs II block with 0.25% bupivacaine to the standard of care of local surgeon infiltration with 0.25% bupivacaine following open subpectoral biceps tenodesis, particularly in terms of duration of pain control and adjunctive postoperative analgesic consumption. The primary objective will be to compare opioid utilization between the two arms within the first 24 hours after surgery, including intraoperatively, as measured by oxycodone equivalents. Our secondary objectives are measuring patient reported pain scores in PACU and at 24 hours, reaction to surgical incision, and skin assessment of sensation in the PACU.

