### **4.2 Study Schedule**

#### **4.2.1 Screening**

##### **Screening Visit (Pre-surgical office visit -30 to -1 days)**

- Review medical history to determine eligibility based on inclusion/exclusion criteria.
- Review medications history to determine eligibility based on inclusion/exclusion criteria.
- Perform medical examinations needed to determine eligibility based on inclusion/exclusion criteria.
- Schedule study visits for participants who are eligible and available for the duration of the study.
- Provide participants with further details regarding their participation on day of surgery and follow up.

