#### **4.2.3 Follow-Up Phone call (POD 1 and POD 3)**

1. Phone call to patient to collect additional data on opioid use following discharge, on POD 1 and 3 after surgery

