### 6.2 Analysis of Endpoints

#### Primary Endpoints:

1. Opioid utilization for the first 24 hours after surgery, including during surgery, calculated as oxycodone equivalent.

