#### 6.2.1 Baseline Descriptive Statistics

The following patient data will be recorded: age, gender, height, weight, date of admission, date of discharge, laterality, surgical approach, implants used, duration of surgery, contamination, ASA, comorbidities (smoking, cardiac history, diabetes etc.), and medications. This information will be accessible in the patient's medical record.

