### 6.3 Sample Size

80 subjects will be enrolled

Based on published reports (Reynolds et al) and our clinical experience, we estimate that patients in the Pecs group will use only 25 mg of oxycodone-equivalent, while patients receiving the infiltration will use 32 mg. Using a 2-sided, 2-sample t test, an  $\alpha$  value of 0.05 and assuming a common SD of 13, a power analysis revealed that 72 subjects were needed per group for a power of 0.90. We chose to enroll 80 subjects per arm to allow for potential dropout and an increased power.

CONFIDENTIAL

This material is the property of the NYU School of Medicine and Langone Medical Center. Do not disclose or use except as authorized in writing by the study sponsor

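### Patients who have used opioids for less than 3 months can enrol, and the primary 24-hour opioid comparison neither stratifies by nor adjusts for preoperative opioid use

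*Combined protocol and SAP*

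**What the plan says.** Section 3.2, exclusion 2, bars "Patients with a history of chronic pain that have used opioids for pain management for 3 months or longer". The nearest other criterion is exclusion 6, "Patients with a history of drug or recorded alcohol abuse", which concerns abuse and not prescribed or short-term use. Exclusion 11 leaves room for investigator judgement, but about compliance with study procedures.

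The primary endpoint in Section 6.2 is "Opioid utilization for the first 24 hours after surgery, including during surgery, calculated as oxycodone equivalent". Section 1.3 gives the same window. Use at home is collected under Section 4.2.3: "Phone call to patient to collect additional data on opioid use following discharge, on POD 1 and 3 after surgery".

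Preoperative medication is not ignored. The screening visit includes the step "Review medications history to determine eligibility based on inclusion/exclusion criteria", and Section 6.2.1 lists "comorbidities (smoking, cardiac history, diabetes etc.), and medications" among the baseline data. Preoperative opioid use is not named as an item, and no dose or recall period is given.

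Randomisation (Sections 2.1 and 6.4) is 1:1 in blocks of four with no stratification factor stated. Section 6.2 compares the primary outcome with a two-sample t-test, or a rank-sum test if the data are not normal. No covariate is specified. Section 6.3 plans for 25 against 32 mg, "assuming a common SD of 13".

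**The concern.** The endpoint counts the same class of drug that some patients may already be taking when they arrive. Someone who has taken oxycodone daily for ten weeks for the shoulder meets no exclusion criterion as written. Neither does someone who has taken it for longer without a chronic-pain history. After surgery such a patient may keep up the usual intake, or need more because of tolerance. Nothing in the plan separates that part of the 24-hour total from use prompted by the new surgical pain, and the choice of block may have little influence on it.

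What is at stake is precision. Variation between patients that comes from prior use enters the primary comparison as noise, although a variable that could explain much of it is close to being collected already.

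**Working it through.** **Inputs from Section 6.3.** Difference 32 − 25 = 7 mg; SD 13 mg; two-sided alpha 0.05; power 0.90; stated need 72 per group; 80 per arm enrolled.

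**The plan's own figure.** By normal approximation, n = 2 × (1.960 + 1.282)² × 13² / 7² = 72.48, or 73 rounded up. The exact t calculation gives 73.45, or 74. The stated 72 is reproduced to within rounding. At 80 per arm the t-test has power 0.923 on these inputs.

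**Assumptions, not in the documents.** A share p of patients in each arm are current users. Each uses d mg more in the counted window, whichever arm they are in. The SD of 13 describes non-users, and the 7 mg difference is unchanged.

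**Formula.** SD = √(13² + p(1 − p)d²). For p = 0.10 and d = 20: √(169 + 0.09 × 400) = √205 = 14.32 mg.

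| Share p | Extra d (mg) | SD (mg) | Power at 80 per arm (t-test) |
|---|---|---|---|
| none | – | 13.00 | 0.923 |
| 5% | 10 | 13.18 | 0.916 |
| 5% | 20 | 13.71 | 0.894 |
| 5% | 30 | 14.55 | 0.856 |
| 10% | 10 | 13.34 | 0.910 |
| 10% | 20 | 14.32 | 0.867 |
| 10% | 30 | 15.81 | 0.795 |

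In the 10%, 20 mg case, 90% power without adjustment would need 89 per arm (exact t).

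**Chance imbalance is part of the same variance.** For p = 0.10 and d = 20, the standard error of the shift in the mean difference caused by unequal numbers of users is 20 × √(2 × 0.10 × 0.90 / 80) = 0.95 mg. Its 95% range is ±1.96 × 0.95 = ±1.9 mg, or 27% of 7 mg. The standard error of the difference at SD 13 is 13 × √(2/80) = 2.06 mg. Together, √(2.06² + 0.95²) = 2.26 mg, which equals 14.32 × √(2/80). The imbalance is therefore already inside the inflated SD and must not be counted again.

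**What adjustment recovers.** In this model the term p(1 − p)d² is entirely between users and non-users. Accurate adjustment for user status would bring the residual SD back to 13, and power to about 0.92. Imperfect reporting would recover less.

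**The case against.** The strongest reply is that nothing here is an error. Where to set the limit on prior opioid use is a design choice, and the rule does remove long-term users with chronic pain. An unadjusted comparison of randomised arms is valid, and its confidence interval already carries the extra variance. That stands: this is a matter of efficiency, not validity.

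The size also rests wholly on assumptions. Section 6.3 takes its figures from published reports and clinical experience and does not say that opioid users were left out. If the SD of 13 reflects a mixed population, the calculated power loss disappears. This too stands.

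It can further be said that the plan would reveal an imbalance. Concomitant medications go on the CRF (Section 4.3), baseline characteristics are compared by standardised difference (Section 6.1), and outcomes are plotted against covariates (Section 6.2). This stands only in part. Seeing an imbalance does not correct for it, and an adjustment chosen after the data are seen is less credible than a prespecified one.

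Some stronger readings are tempting but unsupported:

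- A reader might infer that opioids taken before surgery are scored as outcome. They are not. Section 1.3 sets out to "compare opioid utilization between the two arms within the first 24 hours after surgery, including intraoperatively, as measured by oxycodone equivalents", and home data cover use after discharge. Only use that continues inside the window can count.
- A reader might infer bias towards one arm. Randomisation rules out a systematic effect of prior use.
- A reader might infer that the rule selects on remote history and disregards current exposure. It does exclude current long-term users who have chronic pain.

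**Conclusion.** The point holds as an efficiency gap. Shorter-term opioid users are eligible, their prior use can carry into the primary endpoint, and neither the randomisation nor the primary test uses that information. It is not evidence of bias, and it does not make the sample-size figure wrong.

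Under the assumed 5% to 10% of users and 10 to 30 mg of extra intake, the loss runs from under 0.01 to about 0.13 in power. In three of the six cases tabulated, 80 per arm falls clearly below the planned 0.90 (0.867, 0.856 and 0.795), and in one it falls marginally below (0.894). If users are almost absent, or the SD of 13 already includes them, the loss is negligible. The documents do not allow a choice between these cases. The improvement is worth making because it is cheap and because preoperative intake is hard to reconstruct reliably afterwards.

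**What to change.** In Section 4.2.2, add an item to the Day 0 baseline assessment, completed before randomisation: any opioid use in a stated recent period, and the usual daily amount. Seven days would match the recall period of the PROMIS pain items already attached.

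In Section 6.2, prespecify this variable as a covariate in the primary comparison: ANCOVA, or a rank-sum test stratified by current use if the data are not normal. Add a sensitivity analysis restricted to patients with no current opioid use.

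Exclusion 2 need not be reworded for this purpose. Tying it to current or recent use of 3 months or longer, for example, would still admit the ten-week user.

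The cost is one self-reported CRF item, building on a medication history that is already reviewed, and one covariate in the model. No additional patients are needed. The limitation is that the recorded amount depends on what patients report.

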#### **3.3 Vulnerable Subjects**

No vulnerable populations will be enrolled in this study.

#### **3.4 Recruitment and Consent**

This study will utilize EPIC to identify subjects and use Redcap in addition to the firewall protected shared drive to manage and store relevant data.

##### **Process of Consent**

The consent for participation will be obtained on day of surgery in pre-operative holding room by the regional anesthesiology fellows, Attending Physicians, or authorized researchers that are members of the study team. Extensive discussion of risks and possible benefits of participation will be provided to the participants and their families. Consent forms will be IRB-approved, and participants will be asked to read and review the document. The investigator will explain the research study to the participant and answer any questions that may arise. All participants will receive a verbal explanation suited to their comprehension of the purposes, procedures and potential risks as well as their rights as research participants. Participants will have the opportunity to carefully review the written consent form and ask questions prior to signing. The participants will have the opportunity to discuss the study with their surrogates or think about it prior to agreeing to participate. The participant will sign the informed consent document prior to any procedures being done specifically for the study. The participants may withdraw consent at any time throughout the course of the trial. A copy of the signed informed consent document will be given to the participants for their records. The rights and welfare of the participants will be protected by emphasizing that the quality of their medical care will not be adversely affected if they decline to participate in this study. If you are unable to obtain consent at an earlier time, subjects will be given a copy of the informed consent form at their pre-surgical visit to allow them time to read through it, discuss with their relatives, and contact the study team with any questions prior to their surgery.

CONFIDENTIAL

This material is the property of the NYU School of Medicine and Langone Medical Center. Do not disclose or use except as authorized in writing by the study sponsor

A copy of the signed informed consent document will be given to the patient, placed in the patient's electronic medical record and the original copy will be stored in the research regulatory binder. Any alteration to the standard consent process (e.g., use of a translator, consent document presented orally, etc.) and the justification for such alteration will likewise be documented.

Capacity will be assessed through the subject's ability to express understanding of the information being presented to them. The subject will be asked to state back the goals of the study and that they are willing to participate in their primary language.

If a subject requests information regarding opting out of further recruitment for all research, subjects will be directed to contact the research coordinator, [name] at [name] or [name] at [contact].

### **3.5 Duration of Study Participation**

The study will remain open until 80 patients are recruited for each intervention arm of the study. The actual subject participation length will be four days.

### **3.6 Total Number of Participants and Sites**

Recruitment will end when 160 participants have been enrolled. It is expected that there will be subjects enrolled who will be lost to follow up and be evaluated by intention-to-treat. The sites for enrollment will be the NYU Langone Orthopedic Hospital and NYU Ambulatory Surgery Center at 38th street.

### **3.7 Participant Withdrawal or Termination**

Participants are free to withdraw from participation in the study at any time upon request. An investigator may terminate participation in the study if:

1. Any clinical adverse event (AE), laboratory abnormality, or other medical condition or situation occurs such that continued participation in the study would not be in the best interest of the participant
2. The participant meets an exclusion criterion (either newly developed or not previously recognized) that precludes further study participation

### **3.8 Premature Termination or Suspension of Study**

This study may be temporarily suspended or prematurely terminated if there is sufficient reasonable cause. If the study is prematurely terminated or suspended, the PI will promptly inform the IRB and will provide the reason(s) for the termination or suspension.

Circumstances that may warrant termination or suspension include, but are not limited to:

1. Determination of unexpected, significant, or unacceptable risk to participants;
2. Demonstration of efficacy that would warrant stopping;
3. Insufficient compliance to protocol requirements;
4. Data that are not sufficiently complete and/or evaluable; or
5. Determination of futility

## **4 Study Procedures and Schedule**

### **4.1 Study Procedures/Evaluations**

#### **4.1.1 Study Specific Procedures**

Patients will be screened for eligibility by the surgical team during their pre-surgical office visit. Surgeons will explain the study to the eligible patient.

If patients are agreeable to participation, a research team member will provide further details and ask for participation on day of surgery. Informed consent will be obtained on day of surgery when the patient is in the

CONFIDENTIAL

This material is the property of the NYU School of Medicine and Langone Medical Center. Do not disclose or use except as authorized in writing by the study sponsor

pre-operative holding room by an authorized research member. Patient will complete a baseline global health and pain assessment.

Patients in both groups will receive an interscalene nerve block with 15mL 0.5% bupivacaine. Subjects in the Pecs II block group will receive a Pecs II fascial plane block with 20mL 0.25% bupivacaine. The Pecs II block consists of an injection of 20ml of 0.25% bupivacaine 1:200,000 between the pectoralis minor and the serratus anterior muscles. This will be accomplished using ultrasound guidance to identify the appropriate anatomic structures and ensure appropriate needle localization prior to injection of 20 mL 0.25% bupivacaine 1:200,000.

Postoperatively, pain will be assessed via visual analog scale (VAS) by nursing staff during the post-operative period as per standard of care. The VAS pain scores are collected and documented in the patient's electronic medical record. Additionally, while the patient is in the PACU, an authorized research member will visit the patient and administer a pain questionnaire (NRS and McGill Pain scale). Skin testing in the axilla will be done in PACU prior to discharge. Data on PACU opioid use documented in EPIC will be collected.

#### **4.1.2 Standard of Care Study Procedures**

The subjects receiving standard of care procedures will undergo local surgeon infiltration of the surgical field with 15 mL of 0.25% bupivacaine 1:200,000. The OR nurse will obtain the local anesthetic from the operating room omniceil.

### **4.2 Study Schedule**

#### **4.2.1 Screening**

##### **Screening Visit (Pre-surgical office visit -30 to -1 days)**

- Review medical history to determine eligibility based on inclusion/exclusion criteria.
- Review medications history to determine eligibility based on inclusion/exclusion criteria.
- Perform medical examinations needed to determine eligibility based on inclusion/exclusion criteria.
- Schedule study visits for participants who are eligible and available for the duration of the study.
- Provide participants with further details regarding their participation on day of surgery and follow up.

#### **4.2.2 Enrollment/Baseline**

##### **Enrollment/Day of surgery (Visit 1, Day 0)**

- Obtain informed consent of potential participant verified by signature on study informed consent form.
- Verify inclusion/exclusion criteria.
- Complete baseline global health and pain assessment
- Randomize to Pecs II or surgical infiltration treatment group
- Perform surgery with analgesic intervention determined by randomization
- Record vital signs, opioid usage, results of examinations, other pain assessments.
- Continue observation in PACU preceding discharge, including administration of VAS scores, pain questionnaire, and opioid usage monitoring.

#### **4.2.3 Follow-Up Phone call (POD 1 and POD 3)**

1. Phone call to patient to collect additional data on opioid use following discharge, on POD 1 and 3 after surgery

#### **4.2.4 Withdrawal/Early Termination Visit**

Subjects may discontinue their participation in the study at any time. As there is only a single intervention, and the safety of this is not in question, further follow up will not be required if a subject decides to terminate their participation in the study.

CONFIDENTIAL

This material is the property of the NYU School of Medicine and Langone Medical Center. Do not disclose or use except as authorized in writing by the study sponsor

### **4.3 Concomitant Medications, Treatments, and Procedures**

All concomitant prescription medications taken during study participation will be recorded on the case report forms (CRFs). For this protocol, a prescription medication is defined as a medication that can be prescribed only by a properly authorized/licensed clinician. Medications to be reported in the CRF are concomitant prescription medications, over-the-counter medications and non-prescription medications.

